4.2 Exclusion criteria

Subjects should not enter the study if any of the following exclusion criteria are fulfilled:

1. History of any clinically significant medical, neurologic or psychiatric disease or disorder (other than those previously defined as acceptable for these population) which, in the opinion of the Investigator and sponsor, may either put the subject at risk because of participation in the study, or influence the results of the subject's ability to participate in the study: This includes seizure activity and repeated episodes of major depression.
2. Subjects with a history of suicide attempts in the past year and/or seen by the Investigator as having a significant history of risk of suicide or homicide, or considered at risk for suicide or homicide during the study.
3. History of gastrointestinal surgery (with the exception of cholecystectomy and appendectomy) or unintentional rapid weight loss.
4. Subjects with an active renal transplant (subjects who have previously received a renal transplant and are currently undergoing dialysis due to transplant failure may be enrolled)
5. Any clinically significant acute illness or medical/surgical procedure within 4 weeks of the first administration of investigational product (IP) (other than those previously defined as acceptable for these population) as judged by the Investigator.
6. Clinically significant progression of current disease or clinically relevant trauma, as judged by the Investigator, within 2 weeks before the first administration of the IP.

7. Any clinically significant abnormalities (other than those associated with the subject's degree of renal impairment and /or stable chronic condition) in clinical chemistry, hematology or urinalysis results as judged by the Investigator and Sponsor.
8. A positive result on screening for serum hepatitis B surface antigen or human immunodeficiency virus (HIV).
9. Clinically significant abnormal vital signs as judged by the Investigator
10. Any clinically important abnormalities in rhythm, conduction or morphology including abnormalities suggestive of acute changes or recurrent ischemic changes of resting electrocardiograms (ECG) as determined by the Investigator and sponsor
11. Prolonged QTcF (subjects with up to 500 ms prolongation are acceptable with joint approval with investigator and sponsor) or shortened QTcF (less 340 ms), or family history of Long QT Syndrome
12. Current smokers, those who have smoked or used nicotine products within the previous 1 month prior to enrollment are to be excluded only if the investigative site has no accommodation for subjects to continue smoking during confinement.
13. Consumption of alcohol within 72 hours of admission to the clinic.
14. Past or present alcohol or drug abuse within 1 year of enrollment. Excessive intake of alcohol (greater than 15 units/week).
15. Positive test in drugs of abuse screens (except for prescription medications, which are verified by the Investigator), or alcohol on admission to the clinic prior to the administration of the IP
16. Pregnancy, lactation or positive serum pregnancy test in women at screening and at admission to the unit prior to the first administration of IP.
17. History of severe allergy/hypersensitivity or ongoing allergy/hypersensitivity, other than seasonal allergies, as judged by the Investigator
18. Excessive intake of caffeine containing foods or beverages (more than 5 units or equivalent per day). One caffeine unit is contained in the following items: one (6 oz.) cup of coffee, two (12 oz) cans of cola, one (12 oz) glass of tea, ½ (4 oz) cup of energy drink (e.g. Red Bull) or three (1oz) chocolate bars within 48 hours prior to admission to unit.
19. Plasma or blood product donation within one month of screening or any blood donation/blood loss greater than 500 mL during the 3 months prior to screening or intention to donate blood or blood products during the study or within 1 month after the completion of the study.

20. Has received another new chemical entity (defined as a compound which has not been approved for marketing) other investigational drug product within 30 days (if half-life was less than 24 hours) of the first administration of IP in this study. Note subjects consented and screened but not dosed in previous phase I studies are not excluded.
21. Involvement in the planning and/or conduct of the study (applies to both AstraZeneca staff and/or staff at the study site)
22. Judgment by the Investigator that the subject should not participate in the study if considers subject unlikely to comply with study procedures, restrictions and requirements
23. History or hypersensitivity or intolerance to drugs with a similar chemical structure or class to TC-5214

For control subjects:

24. Use of prescription medication for a chronic medical condition in this demographically matched control group is acceptable as long as the medical condition is stable and there have been no significant changes in the medical regimen within 6 weeks of Day 1 unless approved by the investigator and sponsor. Accepted drugs include hormone replacement therapy, diuretics, ACE inhibitors, statins, NSAIDs and oral hyperglycemic agents. Unaccepted drugs include beta blockers, vasodilators, calcium channel blockers, nitrates and erectile dysfunction drugs, high dose NSAIDs, probenecid, penicillin G, phenylbutazone, and indomethacin

Subjects with renal insufficiency:

25. Subjects may continue their appropriate accepted (as agreed between the Investigator and sponsor) routine medications as long as there have been no recent (within 28 days) significant changes in, or addition to, routine medications. Subjects on beta blockers, vasodilators, or calcium channel blockers may be included at the discretion of the Investigator and considered for an individualized dose reduction when appropriate. Unaccepted drugs include nitrates, erectile dysfunction drugs, high dose NSAIDs, probenecid, penicillin G, phenylbutazone, and indomethacin.

In addition, the following is considered a criterion for exclusion from the genetic research:

26. Previous bone marrow transplant
27. Whole blood transfusion within 120 days of the date of genetic sample collection

Procedures for withdrawal of incorrectly enrolled subjects see Section 5.3.

5. STUDY CONDUCT

5.1 Restrictions during the study

The following restrictions apply from the specified time and throughout the study period:

1. Subjects must fast from at least 2 hours before planned administration of IP. A moderate amount of water is allowed up to 1 hour prior to dosing and may be resumed 1 hour after dosing. A meal may be given as early as 1 hours after dosing. A moderate amount of water is allowed up to 1 hour prior to dosing and may be resumed 1 hour after dosing.
2. Subjects may eat and drink only the standardized diet provided (appropriate for the subject's degree of renal insufficiency) during the residential period in the unit.
3. Subjects should follow instructions with regard to food and fluid intake in relation to samplings of clinical laboratory tests during the study.
4. Abstain from consuming any of the following:
 - Alcohol from 72 hours before admission, during the residential period and for 72 hours before the study follow-up visit
 - Energy drinks containing taurine or glucuronolactone eg, Red Bull from 72 hours before admission, during the residential period and for 72 hours before the study follow-up visit
 - Caffeine-containing drinks during the residential period apart from any provided as part of a standardized meal. Excessive intake of caffeine should be avoided between discharge from the unit and the study follow-up visit
 - Poppy seeds found in specialty bread from time of consent until after the final medical examination at the study follow-up
 - Grapefruit, grapefruit juice, Seville oranges, Seville orange marmalade or other products containing grapefruit or Seville oranges from 72 hours before admission until after the final medical examination at the study follow-up.
5. Unless smoking areas are accessible to subjects who are smokers, abstain from nicotine use, smoking and drugs of abuse from screening until after the final medical examination at the study follow-up.
6. Subjects with normal renal function should adhere to the medication restrictions according to exclusion criteria #24.
7. For subjects with renal insufficiency refer to exclusion criteria # 25.

8. Subjects will remain semi-recumbent or sitting for 4 hours following IP administration.
9. Subjects should refrain from strenuous physical activity, which is not within the subject's normal daily routine, from 48 hours prior to admission to the unit until after the final medical examination at the study follow-up.
10. Abstain from blood or plasma donation until 3 months after the final medical examination at the study follow-up.
11. Abstain from unprotected sex and sperm donation from the first administration of IP until 3 months after the last administration of IP. Subjects should ensure that their partners of child bearing potential use a reliable method of contraception.

5.2 Subject enrollment and initiation of investigational product

The Investigator will ensure:

1. Signed informed consent is obtained from each potential subject before any study specific procedures are performed
2. The eligibility of each subject is determined. See Sections [4.1](#) and [4.2](#).
3. Each screened subject is assigned a unique enrollment number or Ecode (eg E0001001) at screening (before any procedures are completed)
4. Subjects who pass all screening procedures will return to the clinic on Day -1

Subjects in Group 1 who withdraw from the study prior to completion of all PK sample collections may be replaced; subjects in Groups 2 and 3 who withdraw from the study prior to completion of all PK sample collections may be replaced to ensure a minimum of 6 subjects complete the treatment period.

Subjects in Group 5, Part 1, who withdraw from the study after completion of Treatment Period 1 (assessments between dialysis) and before entering Treatment Period 2 (assessments during dialysis) may be replaced at the discretion of the Sponsor (see Section [5.9](#)). Subjects in Group 5, Part 2 may be replaced.

All replacements must be approved by AstraZeneca. If a subject withdraws his/her participation in the study, then his/her enrollment code cannot be reused. Enrollment codes for replacement subjects will be assigned as follows: the original subject's number plus 1000 (eg, if the original subject being replaced had a subject number of 504, the replacement subject's number will be 1504).

5.2.1 Procedures for randomization (Not Applicable)

5.3 Procedures for handling subjects incorrectly enrolled or initiated on investigational product

Subjects who fail to meet the inclusion/exclusion criteria should not, under any circumstances receive study medication. There can be no exceptions to this rule.

Where subjects that do not meet the selection criteria are incorrectly started on treatment, or where subjects subsequently fail to meet the study criteria post initiation, a discussion should occur between the AstraZeneca CPA Physician and the Investigator regarding whether to continue or discontinue the subject from treatment.

The AstraZeneca CPA Physician is to ensure all such decisions are appropriately documented. In situations where an agreement cannot be reached, the subject should have their study treatment stopped.

5.4 Blinding and procedures for unblinding the study (Not Applicable)

5.5 Treatments

5.5.1 Identity of investigational product(s)

AstraZeneca or a company acting on its behalf will supply the IP to the Investigator. The IP will be supplied as tablets for oral use according to the description in Table 3 below.

Table 3: TC-5214

Investigational product	Dosage form and strength	Manufacturer
TC-5214	2 mg Tablet	[REDACTED]
TC-5214	4 mg Tablet	[REDACTED]

The formulation consists of -(+)-mecamylamine hydrochloride (TC-5214) [(1R,2S,4S)-N,2,3,3-tetramethylbicyclo-[2.2.1]heptan-2-amine hydrochloride] provided in hard gelatin tablets at 2 mg dose strengths based on free base equivalents.

5.5.2 Doses and treatment regimens

Investigational product will be administered with 240 mL of water. For details on food and fluid intake surrounding drug administration refer to Section 5.1.

Subjects in Groups 1 and 2 will receive a single dose of TC-5214 8 mg (2 x 4 mg tablets).

Subjects in Groups 3 will receive a single dose of TC-5214 2 mg.

Subjects in Groups 5, Part 1 will receive a single dose of TC-5214 2 mg, on 2 occasions, once during each treatment period. These doses will be separated by a washout period of at least 14 days.

Subjects in Groups 5, Part 2 will receive a single dose of TC-5214 2 mg.

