3.1 Overall study design and flow chart

This is a Phase I single dose, multi center, open-label study designed to evaluate the safety, tolerability and PK of TC-5214 in renally impaired subjects compared with subjects with normal renal function.

Based on an interim review of the safety and pharmacokinetics data, subjects with severe renal impairment (previous Group 4) will not be recruited for this study, and the study will be conducted in 2 parts.

Subjects will be enrolled into 1 of 4 groups in parallel, according to their degree of renal impairment based on their estimated glomerular filtration rate (eGFR), determined using the abbreviated, 4-variable Modification of Diet in Renal Disease (MDRD) formula as follows:

Group 1: control subjects with normal renal function: eGFR greater than 80 mL/min

Group 2: mild renal impairment: eGFR greater than or equal to 50 to 80 mL/min

Group 3: moderate renal impairment: eGFR greater than or equal to 30 to less than 50 mL/min

Group 5: end stage renal disease (ESRD): eGFR less than 30 mL/min, currently receiving dialysis

3.1.1 Part 1

3.1.1.1 Part 1, Groups 1 through 3

Subjects in Groups 1 through 3 will not be on dialysis. They will be admitted to the clinic the morning of Day -1, or on Day -2 at the discretion of the Investigator. Time-matched vital signs will be collected on Day -1. Subjects will then receive a single oral dose of TC-5214 on Day 1 and will remain in the clinic until the completion of the study assessments and procedures scheduled on Day 4. Subjects will return to the clinic for a follow-up visit 7 to 10 days following discharge from the clinic. Subjects in Group 1 who withdraw from the study prior to completion of all PK sample collections may be replaced; subjects in Groups 2 and 3 who withdraw from the study prior to completion of all PK sample collections may be replaced to ensure a minimum of 6 subjects complete the treatment period. During Part 1, subjects in Groups 1 through 3 will have pharmacokinetic blood and urine samples collected through 72 hours postdose.

3.1.1.2 Part 1, Group 5

The first 4 subjects enrolled into Group 5 will participate in 2 treatment periods, and receive a single oral dose of TC-5214 on each occasion. For Treatment Period 1 subjects will be

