^b A single dose of TC-5214 8 mg will be administered for Groups 1 and 2, 2 mg will be administered for Groups 3 on Day 1.

^c Subjects may be admitted to the clinic on Day -2 to allow for the Day 1 time-matched safety assessments at the discretion of the Investigator.

[figure not shown]
^d For subjects in Groups 1 through 3, during Part 1 blood and urine samples are collected through 72 hours postdose, and for Part 2, blood and urine samples are collected through 120 hours postdose.

Figure 2: Study Flow Chart Group 5, Part 1

- ^a Visit 1 may be conducted over 1 or more days during the screening period.
- ^b A single dose of TC-5214 2 mg will be administered to Group 5 on Day 1 of each residential period
- ^c Subjects may be admitted to the clinic on Day -2 to allow for the Day 1 time-matched safety assessments at the discretion of the Investigator.
- ^d At least 14 days between TC-5214 administrations.

Figure 3: Study Flow Chart Group 5, Part 2

- ^a Visit 1 may be conducted over 1 or more days during the screening period.
- ^b A single dose of TC-5214 2 mg will be administered to Group 5 on Day 1.
- ^c Subjects may be admitted to the clinic on Day -2 to allow for the Day 1 time-matched safety assessments at the discretion of the Investigator.

Table 1: Study Plan, Part 1

Visit number	1	2 Residential Period (For Group 5, Part 1 – 2 Residential Periods)					3		
	Activity/ Day	-30 to -2 Screening	-1 ^h	1	2	3	4	Follow-Up 7 to 10 days following discharge	Details in Section
Informed consent	X								8.4
Demography	X								6.2
Inclusion/exclusion criteria	X	X							4
Physical Examination	X	X ⁱ					X ⁱ	X	6.3.6
Height and weight ^a	X	X					X		6.3.6
Medical and Surgical History	X								6.2
Columbia Suicide Severity Rating Scale	X	X					X	X	6.2
Clinical chemistry	X	X					X	X	6.3.5
Hematology	X	X					X	X	6.3.5
Urinalysis	X	X					X	X	6.3.5
HIV and HBV Serology	X								6.3.5
Drugs of Abuse Screen	X	X							6.3.5
Alcohol Screen		X							6.3.5

Visit number	1	2 Residential Period (For Group 5, Part 1 – 2 Residential Periods)					3		
	Activity/ Day	-30 to -2 Screening	-1 ^h	1	2	3	4	Follow-Up 7 to 10 days following discharge	Details in Section
Blood pregnancy test for female subjects of childbearing potential	X	X					X		6.3.5
Orthostatic blood pressure (supine, seated, and standing) and pulse ^b	X	X	X	X	X	X	X	X	6.3.7
Oral temperature and respiration rate	X	X	X	X	X	X	X	X	6.3.5
12-lead ECG ^c	X	X	X				X	X	6.3.6.1
Admission to the clinic		X							NA

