3.2 Rationale for study design, doses and control groups

The purpose of this study is to determine if renal impairment will affect the PK of TC-5214. The study is designed using the principals embodied in the Food and Drug administration guidance on drug renal impairment studies ([Cockcroft 1976](#)).

For control subjects with normal renal function and subjects with mild renal impairment, a 8 mg dose of TC-5214 was chosen because it is the highest daily dose that will be administered in Phase III trials and was shown to be well tolerated in healthy subjects in previous studies. For subjects with moderate and severe renal impairment, to minimize the effects of compensatory changes such as significant hypotension, a 2 mg dose will be administered.

In order to avoid bias due to demographic differences between the control subjects with normal renal function and subjects with renal impairment, the control group will be matched to the mean demographic characteristics of the **3** renal impairment groups with an allowable variability in age of +/- 10 years and in BMI of $\pm 3 \text{ kg/m}^2$. Sex will be matched to achieve similar distribution between male and female subjects. Only control subjects with stable chronic medical conditions will be included.

Based on available data to date, the mean terminal half-life ($t_{1/2,\lambda_z}$) of TC-5214 in human plasma is approximately 8 to 9 hours. Based on limited interim PK data in 2 subjects with moderate impairment, and 2 subjects with ESRD, renal impairment has been shown to increase the half-life of TC-5214 by approximately 3 and 10 fold, respectively.

For Groups 1 to 3, the study design has been updated to extend the sampling period to 120 hours postdose to adequately characterize the elimination phase of TC-5214 and more accurately determine TC-5214 PK parameters (eg $t_{1/2,\lambda_z}$, AUC, and CL/F). For Group 5 it was determined that a single dose of TC-5214 administered after the completion of a dialysis session, with the collection of blood samples for PK through 120 hours postdose (including a 4 hour dialysis session beginning approximately 72 hours postdose) would enhance patient safety.

The PK profile in patients with severe renal failure will be extrapolated from the data in subjects on dialysis obtained between their dialysis sessions, thus subjects with severe renal impairment (eGFR <30 mL/min) will not be recruited for this study.

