11.2 Calculation or derivation of pharmacokinetic variables

The PK analyses of the TC-5214 plasma, urine, and dialysate concentration data will be performed at [REDACTED]. Pharmacokinetic analyses will be conducted according to [REDACTED] SOPs for PK analyses. The actual sampling times will be used in the PK parameter calculations. Pharmacokinetic parameters will be derived using noncompartmental methods with WinNonlin[®] Professional Version 5.2, or higher, (Pharsight Corp., Mountain View, California). All PK computations will be performed using WinNonlin Professional[®] 5.2, or higher; or SAS[®] Version 9.1, or higher (SAS Institute, Inc., Cary, North Carolina). Graphics may be prepared with SAS Version 9.1, or higher; SigmaPlot[®] 9.0, or higher (Systat Software, Inc., San Jose, California); or WinNonlin Professional[®] 5.2, or higher. Nominal times will be used for any interim PK analyses, if applicable.

Where possible, the following plasma PK parameters will be determined for TC-5214:

- Maximum plasma concentration (C_{max} , ng/mL), obtained directly from the observed concentration versus time data

- Time to maximum plasma concentration (t_{\max} , h), obtained directly from the observed concentration versus time data
- Terminal rate constant (λ_z). Visual assessment will be used to identify the terminal linear phase of the concentration-time profile. A minimum of 3 data points, with an Rsq of greater than or equal to 0.8 will be used for determination.
- Terminal half-life ($t_{1/2\lambda_z}$, h)
- Area under the plasma concentration-time curve from zero to the time of the last measurable concentration [$AUC_{(0-t)}$]
- Area under the plasma concentration-time curve from 4 to 8 hours [$AUC_{(4-8)}$] to match the dialysis period, Group 5, Treatment Period 2, Part 1, only
- Area under the plasma concentration-time curve from 72 to 76 hours [$AUC_{(72-76)}$] to match the dialysis period, Group 5, Part 2, only
- Area under the plasma concentration-time curve from zero to infinity (AUC) calculated by linear up/log down trapezoidal summation and extrapolated to infinity by addition of the last quantifiable concentration divided by the elimination rate constant: $AUC_{(0-t)} + C_{\text{last}}/\lambda_z$. If the extrapolated area ($C_{\text{last}}/\lambda_z$) is greater than 30% of AUC, then AUC will not be reported
- Apparent plasma clearance (CL/F, L/h)
- Apparent volume of distribution (V_z/F , L)

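### Group 5 Part 1: the 14-day minimum between doses is only 3.7 to 4.2 half-lives at the ESRD half-life implied by Section 3.2, and the plan does not say how first-dose residual in Period 2 is checked or handled

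*Supplement*

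**What the plan says.** Section 3.1.1.2: "The first 4 subjects enrolled into Group 5 will participate in 2 treatment periods". The order is fixed. Period 1 is dosed after a dialysis session and sampled until the next one; Period 2 is dosed 4 h before a session. Section 5.5.2 sets the gap: "These doses will be separated by a washout period of at least 14 days". The note to Figure 2 counts it from dose to dose: "At least 14 days between TC-5214 administrations".

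Section 3.2 puts the mean terminal half-life "of TC-5214 in human plasma is approximately 8 to 9 hours". From 2 moderate and 2 ESRD subjects it then reports that "renal impairment has been shown to increase the half-life of TC-5214 by approximately 3 and 10 fold, respectively".

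Section 6.4.1.1 draws a predose sample in both periods and samples Part 1 to 72 h. Section 11.2 takes Cmax as "obtained directly from the observed concentration versus time data", builds AUC from AUC(0-t) plus an extrapolated tail, and does not report AUC when the tail exceeds 30%. Neither 11.2 nor 12.2.3 gives a predose check, a baseline subtraction or a carryover criterion. Section 12.2.3 compares the two periods by a paired t-test on Cmax and AUC.

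**The concern.** Fourteen days is ample at the general half-life. It is much less so at the ESRD half-life that Section 3.2 now reports, and nothing in 5.5.2, 11.2 or 12.2.3 takes that up. Period 2 is the dialysis period for every subject, so carryover acts in one direction and no balancing of sequence cancels it: it raises the on-dialysis values. At stake is the between-period comparison serving the hemodialysis objective, together with the dialysate recovery in Period 2, where first-dose drug is credited to the second dose.

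**Working it through.** The documents give no half-life count or residual for the washout, so there is no planned figure to reproduce.

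**Inputs from the protocol.** Half-life 8 to 9 h and a multiple of about 10 in ESRD (3.2), giving 80 to 90 h. Minimum dose-to-dose gap 14 × 24 = 336 h (5.5.2; Figure 2 note). Dialysis from 4 to about 8 h in Period 2 (3.1.1.2; 6.4.1.1). Sampling to 72 h.

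**Assumptions.** First-order, one-compartment kinetics. Group 5 subjects have "eGFR less than 30 mL/min, currently receiving dialysis", so sessions also fall in the washout, but neither their number nor the share r removed per session is stated. I take 4 to 6 sessions. Four follows from the longest gap the design shows, a "4 hour dialysis session beginning approximately 72 hours postdose" in Part 2 (336/72 = 4.7); six assumes three a week. The same r is used for the study session. The AUC ratios treat absorption as instantaneous.

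**Half-lives elapsed.** 336/80 = 4.20; 336/90 = 3.73. At 8 to 9 h it would be 42 to 37. Five half-lives, a common yardstick that the protocol does not state, is 400 to 450 h (16.7 to 18.8 days).

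**Residual with no intervening dialysis.** 2^(−336/80) = 5.4%; 2^(−336/90) = 7.5%. This is the ceiling at those half-lives.

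**Residual with dialysis, and its effect.** With s sessions, c = 2^(−336/t½) × (1 − r)^s. The residual behaves as an extra dose c given at time zero, so the observed Period 2/Period 1 ratio is the true ratio × (1 + c). The share of the true reduction hidden is c × ratio/(1 − ratio). Ranges cover 80 to 90 h and 4 to 6 sessions:

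| r per session | Residual c | True AUC(0-72) ratio | Observed ratio | Share of reduction hidden |
|---|---|---|---|---|
| 5% | 4.0–6.1% | 0.96 | 0.99–1.01 | 86–131% |
| 10% | 2.9–4.9% | 0.91 | 0.94–0.96 | 30–50% |
| 20% | 1.4–3.1% | 0.82 | 0.83–0.85 | 7–14% |
| 30% | 0.6–1.8% | 0.73 | 0.74 | 2–5% |
| 50% | 0.1–0.5% | 0.55 | 0.55 | under 1% |

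Example at 80 h, 4 sessions, r = 10%: c = 0.0544 × 0.9^4 = 0.0357; 0.911 × 1.0357 = 0.943; hidden share 0.0357 × 0.911/0.089 = 0.365.

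**Cmax.** If the peak falls before dialysis starts at 4 h (tmax is not given; sampling is dense from 1 to 3 h), dialysis barely changes Cmax. Carryover then appears as a spurious rise of about c, roughly 0 to 6%, not as a hidden reduction.

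**AUC to infinity.** The tail beyond 72 h in Period 1 is 2^(−72/80) = 54% to 2^(−72/90) = 57%. In Period 2 it is 51 to 57% for r from 10 to 50%. Both exceed the 30% limit, so AUC would mostly go unreported in both periods. AUC(0-t) would still be derived, but it is not a variable in the paired test.

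**Dialysate.** Ad(4-8) and fd(4-8) rise by the factor (1 + c). AUC(4-8) rises by the same factor, so CL_D = Ad(4-8)/AUC(4-8) is unchanged under linear kinetics.

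**The case against.** The case on the other side is substantial. The half-life comes from 2 ESRD subjects; if they were sampled to 72 h, that covers at most 72/80 = 0.9 of a half-life. Fourteen days is a minimum, and dialysis during the washout removes drug. The effect is partly self-limiting: the better the drug is dialysed, the less carries over. All this stands, and it is why 5 to 8% is a ceiling and not an estimate.

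A reader might infer that carryover wipes out the dialysis effect. The table shows that only near r = 5%, where true and observed ratios (0.96 against 0.99–1.01) both say that dialysis removes little. The documents give no dialysability to support that case over the others. A reader might also infer that the hemodialysis objective depends on this contrast alone. It does not: Part 2 gives between-dialysis and during-dialysis data in the same subject after a single dose, with no earlier dose to carry over.

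Precision is poor as well. With 4 pairs and an assumed within-subject CV of 10 to 20%, the 90% CI half-width on the log scale is 2.353 × s × √2/√4, with s = 0.0998 to 0.198, or 0.17 to 0.33. A shift of 0.03 to 0.06 lies well inside it. That limits the practical weight but does not remove the bias, which all 4 subjects share in the same direction.

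Finally, handling of a nonzero predose value may sit in the vendor's PK procedures that 11.2 cites. Those are not shown, and a choice that affects a planned comparison is better stated in the plan.

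**Conclusion.** The point holds in limited form. At the protocol's own ESRD half-life the minimum gap is 3.7 to 4.2 half-lives, and the plan leaves unused the predose sample that would show whether this matters. Following 11.2 as written biases Period 2 Cmax, AUC(0-t), Ad(4-8), fd(4-8) and any reportable AUC upward by at most about 5 to 8%. With 4 to 6 intervening sessions the bias is about 3 to 5% at 10% removal per session, 1 to 3% at 20% and under 0.5% at 50%. It is material only if the drug is poorly dialysed. CL_D and the Part 2 results are not affected. The sizes rest on first-order kinetics, an uncertain half-life, and an assumed session count and removal share. The documents do not show that the washout invalidates the comparison or that any particular washout would be right.

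**What to change.** Analysis text only, in 11.2 and 12.2.3, for Group 5 Part 1 Treatment Period 2:

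- List each subject's predose concentration, and express it as a percentage of Period 2 Cmax.
- Where it is quantifiable, subtract predose concentration × exp(−λz × t) from each later concentration, with λz from that subject's Period 1. Scale the residual after 4 h by the observed dialysis reduction. Derive corrected Cmax, AUC(0-t) and, where reportable, AUC. Reduce Ad(4-8) and fd(4-8) by the residual's share of AUC(4-8).
- Treat a predose value below LLOQ as needing no correction.
- Repeat the paired comparison on the corrected values and show it beside the uncorrected one.

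The predose value measures the residual directly, so neither the session count nor the dialysability has to be assumed. The samples are already scheduled, and the cost is some programming and an extra table. The downside is that λz is imprecise when estimated over less than one half-life, which is why both versions should be reported and neither replaced. No change of washout or dose is proposed; the sponsor should reconcile the washout in 5.5.2 with the ESRD half-life in 3.2.
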